This study was approved by the Institution Review Board (IRB) at the University of Alabama at Birmingham (IRB-300005407-006). All participants signed an informed consent form prior to their inclusion in this study. Nineteen individuals in the chronic phase of recovery after stroke were included in this parallel pilot randomized trial of a robotic treadmill gait protocol combined with behavior management strategies.

All participants received a 6-week intervention that consists of 30–60 minutes of Treadmill Training (TT) sessions, depending on the individual's endurance. The experimental group also received a group of behavioral strategies called the “transfer package” (TP) for 30 minutes after each training session. On the first day of the intervention, the control group (TT) received a handbook with exercises and stretching techniques suggested by the American Stroke Association (ASA). Participants were assessed immediately before and after the intervention, as well as 3 and 6 months after the intervention. All participants received the same TT, which consisted of 18 sessions distributed over 6 weeks (Figure 1). The TT sessions were divided into endurance, strength, and walking speed training, with six sessions for each of these modalities (Figure 1).

[figure not shown]
Figure 1. Modalities of Treadmill Training

The intervention group (TT+TP) received the TT combined with the TP (Figure 2). The original TP is an element of the well-established Constraint-induced Movement Therapy. Participants were asked to sign the behavioral contract (BC). The purpose of the BC is to

ensure that participants: (1) perform tasks with the affected LE in a safe manner, (2) increase use of the more-affected LE in daily tasks, and (3) increase coordination between both LEs. Additionally, the behavioral contract formally engages the patient in actively exploring more ways to use their more-affected LE outside the clinical setting and in adopting a problem-solving approach to accomplish that end.

Figure 2. Combined intervention model

During the 6-week intervention and after every TT session, a new HSA was developed. Each list included up to 10 tasks or exercises to be performed daily between the TT sessions. The list was reviewed at the next session by the therapist, to check: 1) if all activities were performed and 2) if there was any challenge in the participant's performance that should be addressed (e.g., level of difficulty of the task and safety).

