The use of the affected limb was assessed in all treatment sessions through the administration of the LE-MAL. A full description of the LE-MAL is provided in the outcomes section.

The last component of the TP is the Home Practice (HP), which is a list of exercises that the participant should do daily after the end of the treatment period. This list was given to the participant at the end of the last day of the intervention. The purpose of the HP is to assure continued progress with LE use after the intervention program is completed. The expectation was that engagement in home practice would help individuals maintain the changes observed due to the intervention.

The control group (TT) received the same treadmill training described above and also received a list of exercises at the beginning of the intervention (i.e., session 1). The handouts were based on videos provided by the American Stroke Association (available at <https://www.stroke.org/en/life-after-stroke/stroke-rehab/post-stroke-exercise-videos>). All participants received the same list of exercises.

2. Statistical Analysis Plan

An initial sample of 24 individuals would be selected for this pilot trial. However, due to time and recruitment constraints faced by the PI during the SARS-COVID pandemic, this sample size dropped. A total of 19 people with chronic stroke were selected and were randomly allocated using a 2:1 ratio to either TT+TP (N = 12) or TT group (N=7). Individuals were allocated using an online randomization tool (randomization.com, first generator).

The primary outcomes were the Lower Extremity Motor Activity Log (LE-MAL), Berg Balance Scale (BBS), 10 Meter Walking Test (10MWT), and 6-minute walking test (6MWT). The secondary outcomes were: 5 times sit to stand (5TSTS), and the Fear of Falling Avoidance Behavior Questionnaire (FFABQ).

Assessments were administered pre- and post-treatment, and at follow-up visits (3 and 6 months after the end of the intervention protocol). Each assessment visit lasted approximately 60 minutes and was conducted by a physical therapist blinded to group assignment.

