Demographic characteristics including age, gender assigned at birth, chronicity, ethnicity, race, and NeuroQoL score were reported by frequency (%) mean and standard deviation, or range. Due to the small sample size, a descriptive analysis was conducted, and results are shown in mean scores and standard deviation in each time point. The average scores at post-treatment, 3 months follow up and 6 month follow up visit were compared to the average scores obtained at pre-treatment. The differences were compared to the Minimal Clinically Importance Difference (MCID), or Minimal Detectable Change (MDC) of each outcome, if reported in the literature, to identify

significant changes since statistical analysis was not conducted due to the small sample size.

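### The plan compares each later visit only with pre-treatment and a published threshold, so it never estimates the randomised contrast (TT+TP versus TT plus handbook)

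*Combined protocol and SAP*

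**What the plan says.** Section 1, Study Protocol, describes a "parallel pilot randomized trial of a robotic treadmill gait protocol combined with behavior management strategies". All participants have the same 18 treadmill sessions over 6 weeks. The experimental arm also has the transfer package for 30 minutes after each session. The control arm has an exercise handbook, given on the first day.

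Section 2, Statistical Analysis Plan, reports 2:1 allocation giving 12 and 7 participants. It names four primary and two secondary outcomes, assessed before and after treatment and at 3 and 6 months, and says that each assessment "was conducted by a physical therapist blinded to group assignment".

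The outcome analysis is at the end of section 2. It is descriptive: "results are shown in mean scores and standard deviation in each time point". Then: "The average scores at post-treatment, 3 months follow up and 6 month follow up visit were compared to the average scores obtained at pre-treatment". Those differences are compared with an MCID or MDC, where one has been published, to identify "significant changes since statistical analysis was not conducted due to the small sample size".

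Neither section gives a difference between arms, a confidence interval or a model with a treatment term. The analysis paragraph does not mention the arms.

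**The concern.** A control arm, randomisation and blinded assessment all serve one quantity: the difference between TT+TP and TT. The plan does not estimate it. Change from pre-treatment combines the effect of treadmill training, practice on the tests, the passage of time and any effect of the transfer package. If the averages are pooled, the two arms are merged. If they are by arm, a reader could subtract the means, but the plan itself offers neither that estimate nor its uncertainty.

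The MCID/MDC comparison takes the place of inference, since it is what the plan uses to call a change significant. It answers a different question. Whether an arm passes depends on where its change lies relative to the threshold, not on how far the arms are apart. Two equal arms can therefore receive different verdicts, and two different arms the same verdict. At stake is whether the report can say anything about the transfer package, for every outcome at every visit.

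**Working it through.** **Inputs from the documents.** 12 and 7 randomised (12 + 7 = 19); 24 planned, which is 16 and 8 at 2:1. The plan states no SD, correlation, alpha, power, effect size or threshold value, so it has no figure of its own to reproduce beyond the allocation. Results are in SD units, and the assumptions are marked.

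**1. Precision of the arm difference in change.** Half-width of the 95% interval = t(0.975, n1+n2−2) × √(1/n1 + 1/n2), in units of the SD of change.

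| Numbers | √(1/n1+1/n2) | t | Half-width |
|---|---|---|---|
| 12 v 7 (actual) | 0.4756 | 2.110 | 1.00 |
| 16 v 8 (planned) | 0.4330 | 2.074 | 0.90 |
| 10 v 5 (assumed losses at follow-up) | 0.5477 | 2.160 | 1.18 |

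The shortfall from 24 to 19 widens the interval by 1.003/0.898 = 1.12, about 12%. Power of a two-sided 5% t-test at 12 v 7 is about 35% for a true difference of 0.8 SD. A test would be weak, but an estimate is feasible.

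**2. Effect of baseline adjustment.** In units of the outcome SD, with equal variances and an assumed pre-post correlation r:

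- ANCOVA: t(0.975, 16) × 0.4756 × √(1−r²), with t = 2.120
- Difference in change: t(0.975, 17) × 0.4756 × √(2(1−r)), with t = 2.110

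| r (assumed) | ANCOVA | Difference in change |
|---|---|---|
| 0.6 | 0.81 | 0.90 |
| 0.8 | 0.60 | 0.63 |
| 0.9 | 0.44 | 0.45 |

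Chance baseline imbalance widens the ANCOVA figures by about 3% on average (factor 1.032, by simulation). The gain from ANCOVA is therefore small once r reaches 0.8.

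**3. Threshold verdicts when the arms are truly equal.** Let k = true mean change ÷ threshold and s = SD of change ÷ threshold (both assumed). An arm of size n passes with probability P(n) = Φ((k−1)√n / s). The arms disagree with probability P(12)(1−P(7)) + P(7)(1−P(12)). For example, at k = 1.5 and s = 1, P(12) = 0.958 and P(7) = 0.907, so disagreement = 0.958 × 0.093 + 0.907 × 0.042 = 0.127.

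| k | s = 0.5 | s = 1 | s = 2 |
|---|---|---|---|
| 1.0 | 50% | 50% | 50% |
| 0.75 or 1.25 | 13% | 35% | 46% |
| 0.5 or 1.5 | 0.4% | 13% | 35% |
| 2 | about 0% | 0.4% | 13% |

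**4. Threshold verdicts when the arms truly differ by 1 SD (s = 1).**

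| True change, TT+TP / TT (× threshold) | TT+TP passes, TT does not |
|---|---|
| 1.5 / 0.5 | 87% |
| 2 / 1 | 50% |
| 2.5 / 1.5 | 9% |

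The true difference is the same in all three rows. In the last row both arms pass in 91% of trials, and the difference goes unseen.

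**The case against.** This is a pilot, and it openly limits itself to description because it is small. That is a fair reason to omit hypothesis tests. It is not a reason to omit a difference with an interval, which is itself descriptive.

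The plan is silent on arms, so tables may in practice be by arm. Means, SDs and arm sizes would then let a reader derive a crude difference in visit scores and a two-sample interval, given complete data or the numbers at each visit. That stands, and it narrows the loss if tables are by arm. But the text does not promise such tables, and a reader's own calculation is not a planned estimate. The SDs at each visit also do not give the SD of change without the pre-post correlation, so the interval for a difference in change or a baseline-adjusted difference could not be recovered.

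The stated aim speaks of the effect of gait training with the transfer package and does not say versus training alone. Change from pre-treatment describes that aim directly, but a randomised control arm still implies the contrast.

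No passage says the package will be judged by one arm passing and the other not. The disagreement rates therefore show why such a reading would fail. They do not measure an error already made, and they run from about 0% to 50% with the assumptions.

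Finally, six outcomes at three visits give 18 intervals, of which about 18 × 0.05 = 0.9 would exclude zero with no true effect. That calls for a caveat, not for leaving the contrast out.

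**Conclusion.** The concern holds. An analyst following section 2 exactly would produce no estimate of what the transfer package adds to treadmill training, for any outcome at any visit. The small sample does not explain the gap: the interval is wide, about ±1.00 SD of change with complete data, but only about 12% wider than at the planned size.

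The absence of the contrast is read directly from the text and needs no assumption. The half-widths assume a common SD in the two arms, and the 1.00 SD figure assumes no missing visits. The ANCOVA and threshold figures rest on assumed correlations, SDs and true changes, shown as ranges because the documents give none. This should be corrected before the results are used to say anything about the transfer package.

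**What to change.** Report the mean, SD and mean change by arm at each visit, with the number contributing, and say how missing visits were handled. Then add text such as:

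> In an exploratory analysis added after the original analysis (post hoc), the TT+TP minus TT difference for each outcome at post-treatment, 3 and 6 months was estimated by ANCOVA on the pre-treatment score, with participants in their randomised arm, and is shown with its 95% CI. No conclusion rests on p-values. The 18 intervals are not adjusted for multiplicity, and about one would be expected to exclude zero by chance alone. The comparison is TT+TP, including 30 extra minutes per session, versus TT plus exercise handbook. Within-arm MCID/MDC comparisons are descriptive, and no claim about the TP rests on one arm passing a threshold while the other does not.

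Keep the statement that no statistical analysis was done, qualified as applying to the original analysis, and note that the arm difference was added later. A simple difference in change with its interval would be an acceptable alternative to ANCOVA where the pre-post correlation is high.

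The cost is a short re-analysis of data already held (19 participants, four visits) and a few sentences. The intervals will be wide, so the result is an estimate for planning a larger trial and not a verdict on the package. The estimate also cannot separate the content of the package from the extra contact time.

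### Comparing visit averages, with no rule for participants who attend but cannot do a test, can make lost ability look like improvement and gained ability look like worsening

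*Combined protocol and SAP*

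**What the plan says.** Section 2 (Statistical Analysis Plan) is purely descriptive: "results are shown in mean scores and standard deviation in each time point". The comparison over time is between averages: "The average scores at post-treatment, 3 months follow up and 6 month follow up visit were compared to the average scores obtained at pre-treatment". The reading rule follows: "The differences were compared to the Minimal Clinically Importance Difference (MCID), or Minimal Detectable Change (MDC) of each outcome, if reported in the literature". This is meant to identify "significant changes since statistical analysis was not conducted due to the small sample size", so no test or interval stands behind it.

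The participants were "randomly allocated using a 2:1 ratio to either TT+TP (N = 12) or TT group (N=7"). The primary outcomes are the LE-MAL and "Berg Balance Scale (BBS), 10 Meter Walking Test (10MWT), and 6-minute walking test (6MWT"). For the others, "The secondary outcomes were: 5 times sit to stand (5TSTS") and the FFABQ. Assessments are before and after treatment, and 3 and 6 months after treatment ends.

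The text does not say whether the averages at two visits use the same people, how a participant who is present but unable to do a test is scored, or that the number unable is reported. Nor does it say that every participant could do every test.

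**The concern.** A difference between two visit averages equals the average change only if the same people are in both. A performance test offers a particular way to break that. Someone who attends but cannot stand five times has no 5TSTS time, and someone who cannot walk the course has no 10MWT time. With no scoring rule, the natural outcome is a blank, and the person leaves that visit's average. The people affected are likely to be the most impaired, so their departure flatters the average and their arrival depresses it.

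This differs from a missed visit. The participant was assessed, and the inability is itself the result. Section 1 (Study Protocol) names long-term retention of improvement as an aim, so losing an ability by 3 or 6 months is something the trial should be able to show. In arms of 12 and 7, one person can move the mean appreciably, and the comparison with the MCID or MDC is the only decision rule.

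**Working it through.** **Inputs.** The arm sizes, 12 and 7, are from section 2. I take the averages to be computed by arm, which the plan implies but does not state. The documents give no outcome values and no MCID or MDC figures, so all test values below are assumptions. There is no figure in the plan to reproduce.

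**Formula.** Let an arm have n participants. At the first visit, n − 1 of them average m and one has value x. At the second visit the n − 1 are unchanged and the one cannot do the test and is left out.

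- First average: ((n − 1)m + x)/n
- Second average: m
- Apparent change: m − ((n − 1)m + x)/n = (m − x)/n

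Whenever x is worse than m, this is a move in the favourable direction, although nobody improved and one person lost the ability. If that person instead gains the ability and enters at x, the change is (x − m)/n: the same size, now unfavourable. The result does not depend on whether high or low is good. On a standardised scale, someone k SDs worse than the rest shifts the mean by k/n; for k = 2 that is 2/7 = 0.29 SD and 2/12 = 0.17 SD. The smaller control arm is distorted more by a single person.

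**One person loses the ability and is left out; the others do not change.**

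| Test | Others (m) | That person (x) | n = 7 | n = 12 |
|---|---|---|---|---|
| 5TSTS, s | 18 | 25 | −7/7 = −1.00 | −7/12 = −0.58 |
| 5TSTS, s | 18 | 30 | −12/7 = −1.71 | −12/12 = −1.00 |
| 5TSTS, s | 18 | 40 | −22/7 = −3.14 | −22/12 = −1.83 |
| 10MWT, m/s | 0.6 | 0.2 | 0.4/7 = +0.057 | 0.4/12 = +0.033 |
| 10MWT, m/s | 0.8 | 0.2 | 0.6/7 = +0.086 | 0.6/12 = +0.050 |
| 10MWT, m/s | 0.8 | 0.1 | 0.7/7 = +0.100 | 0.7/12 = +0.058 |
| 6MWT, m | 280 | 120 | 160/7 = +22.9 | 160/12 = +13.3 |
| 6MWT, m | 280 | 40 | 240/7 = +34.3 | 240/12 = +20.0 |

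Every entry reads as improvement.

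**One person gains the ability while the others truly improve.** Suppose the others go from 16 s to 14 s on 5TSTS, and one person goes from unable to x. The average moves from 16 to (14(n − 1) + x)/n. It looks worse when x exceeds 16 + 2(n − 1), which is 28 s for n = 7 and 38 s for n = 12. With x = 40 s and n = 7, it is (84 + 40)/7 = 17.7 s against 16.0 s: an apparent loss of 1.7 s although all seven are better off.

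**What the alternatives do.**

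- Scoring inability as 0 on a speed or distance scale gives a change of −x/n, which has the right sign. For 10MWT with x = 0.2 m/s it is −0.029 (n = 7) and −0.017 (n = 12). For 6MWT with x = 80 m it is −11.4 m and −6.7 m.
- Averaging within-person change among those scored at both visits gives 0 in the loss cases and −2 s in the gain case. The false shift is gone, but the lost or gained ability is invisible unless it is counted separately.
- On a scale of seconds 0 cannot be used, because it would be the best possible score.

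**The case against.** The strongest reply is that the plan contains no rule to leave such participants out; it is silent. That is right. A reader might infer that the plan excludes them, or that someone in this trial did become unable, and neither is supported. The session length "depending on the individual's endurance" concerns treadmill training, not ability on the tests, so it is only weak evidence that inability was likely. The text has no eligibility criteria, and it refers to an outcomes section that gives no more detail here, so an entry requirement or scoring convention can be neither confirmed nor ruled out.

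Second, the exposure is limited. The BBS is a graded scale and the LE-MAL and FFABQ are self-reports; these are little affected. A participant who stops early on the 6MWT still has a distance, and 0 is available for distance and for speed. The clear cases are 5TSTS, a secondary outcome, and 10MWT if it is kept in seconds. This stands.

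Third, a shift in the mean, or even a change of its sign, is not the crossing of an MCID or MDC. Those values are not given, so an effect on the trial's conclusions is not shown. This also stands.

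Fourth, this is a small descriptive pilot. That lowers the stakes but does not answer the point: with no inferential analysis, the difference of averages is all there is to read.

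**Conclusion.** The point holds as a weakness of the planned comparison, conditional on someone being able at one visit and unable at another. If that happens and the score is left blank, one worse-than-average performer moves the arm mean in the wrong direction by (m − x)/n. On the assumed 5TSTS values this is 1.0 to 3.1 s in the arm of 7 and 0.6 to 1.8 s in the arm of 12. It matters most for 5TSTS and for 10MWT in seconds, less for 6MWT, and little for the BBS, LE-MAL and FFABQ.

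A reader might go further and conclude that the results are biased, or that the problem arises only on tests where a lower score is better. The documents support neither. They report no inability and no threshold crossing, and the speed and distance rows above show the same effect where higher is better. If nobody was ever unable, stating that count settles the matter.

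**What to change.** Replace the difference of visit averages by the mean within-person change from pre-treatment, among participants scored at both visits, by arm and with the number contributing. Then:

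- Express 10MWT as speed and 6MWT as metres, with 0 for a participant who attends but cannot walk the test. Reserve blanks for missed visits.
- Keep 5TSTS in seconds among those able at both visits, so that it can still be set against an MCID or MDC reported in seconds.
- Always report beside it, by arm and visit, the number unable and the numbers who lost or gained the ability since pre-treatment.
- Optionally add stands per second (5/time, 0 if unable) as a sensitivity analysis. Making it the main 5TSTS analysis is debatable, because it would take that outcome off a threshold expressed in seconds.

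The cost is a few lines in the SAP and a small recode, which is possible only if the reason for each blank score was recorded; the documents do not say that it was. 5TSTS in seconds will still miss gained or lost ability, so the counts have to be read with it. The SAP describes its analysis in the past tense, so the change should be labelled as made afterwards and shown next to the planned comparison.

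### Mean changes are called significant when they reach a published MCID or MDC, a rule that ignores both the SD of change and the number of participants

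*Combined protocol and SAP*

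**What the plan says.** The last paragraph of Section 2 (Statistical Analysis Plan) calls the analysis descriptive because the sample is small, and states that "results are shown in mean scores and standard deviation in each time point". It then sets out the comparison: "The average scores at post-treatment, 3 months follow up and 6 month follow up visit were compared to the average scores obtained at pre-treatment". The criterion follows: "The differences were compared to the Minimal Clinically Importance Difference (MCID), or Minimal Detectable Change (MDC) of each outcome, if reported in the literature". Its stated purpose is to identify "significant changes since statistical analysis was not conducted due to the small sample size".

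The same section gives 12 participants allocated to TT+TP and 7 to TT, four primary and two secondary outcomes, and assessments before treatment, after treatment, and 3 and 6 months later. It gives no MCID or MDC value for any outcome, no SD of change and no confidence interval. It does not say whether the means are taken by arm; I read them so.

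**The concern.** The threshold is offered as the substitute for statistical analysis, and it is the plan's only basis for calling a change significant. Whether a mean change can be told apart from no change depends on the SD of change and on n, and neither enters the rule. The same verdict can therefore carry different evidence in the arm of 12 and the arm of 7.

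The two kinds of threshold fail differently.

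- **MDC.** It is built as a limit for one person's change. Applied to a mean it is usually too strict, so a real average change can be dismissed.
- **MCID.** Setting a mean beside it to describe size is acceptable. Using it to decide significance is not, because an MCID that is small relative to the SD of change can be reached by chance.

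**Working it through.** **Inputs.** From Section 2: n = 12 and n = 7, and the rule that an observed mean change reaching the threshold is significant. The plan states no figure that could be reproduced here. Assumptions: the SD of change (a range is shown), the MDC set at the 95% level, and roughly normal changes. The t quantiles are t(11) = 2.201 and t(6) = 2.447.

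**1. MDC applied to a mean.** Let the error SD be √2 × SEM, where SEM is the standard error of measurement, so that MDC = 1.96 × error SD.

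- Limit for a mean against measurement error alone: MDC/√n, that is 1/√12 = 0.29 and 1/√7 = 0.38 × MDC.
- Let the SD of change be k × error SD. The smallest mean whose 95% t interval excludes zero is t × k/(1.96√n) × MDC. At k = 1 this is 2.201/(1.96 × 3.464) = 0.32 and 2.447/(1.96 × 2.646) = 0.47 × MDC. At k = 2 it is 0.65 and 0.94 × MDC.
- The full MDC stops being stricter than that interval once k exceeds 1.96√n/t = 3.1 (n = 12) or 2.1 (n = 7). For an MDC at the 90% level, 1.645 replaces 1.96 and the limits are 2.6 and 1.8.
- Take k = 1 and a true mean change of half the MDC. The chance that the rule labels it significant is 1 − Φ(0.98√n) = 1 − Φ(3.39) = 0.03% (n = 12) and 1 − Φ(2.59) = 0.5% (n = 7). A one-sample t-test would detect it with 87% and 58% power.

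**2. MCID applied to a mean.** Let s = SD of change/MCID.

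- A mean exactly at the MCID has a 95% t interval that includes zero once s exceeds √n/t = 3.464/2.201 = 1.57 (n = 12) or 2.646/2.447 = 1.08 (n = 7).
- With no true change, the chance that the mean reaches the MCID is 1 − Φ(√n/s):

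| SD of change / MCID | n = 12 | n = 7 |
|---|---|---|
| 1 | 0.03% | 0.4% |
| 1.5 | 1.0% | 3.9% |
| 2 | 4.2% | 9.3% |
| 3 | 12.4% | 18.9% |

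Simulation with 200,000 runs per cell agreed at ratios 1, 2 and 3. A 95% interval on mean change wrongly excluded zero in favour of improvement about 2.5% of the time in all six of those cells.

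These two results use different standards: the first is a two-sided t interval, the second a one-sided normal probability. At ratios of 1.57 and 1.08, where the interval just touches zero, the chance rates are 1 − Φ(2.201) = 1.4% and 1 − Φ(2.447) = 0.7%.

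**3. Can a reader repair this from the reported SDs?** With the same SD S at both visits and pre-post correlation r, the SD of change is S√(2(1 − r)): 1.00 S at r = 0.5 and 0.447 S at r = 0.9. The 95% CI half-width for mean change, t/√n times this, is 0.64 S and 0.28 S for n = 12, and 0.92 S and 0.41 S for n = 7. That is a 2.2-fold range (1.00/0.447) which time-point SDs cannot narrow.

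**The case against.** The strongest reply is that this is a pilot with an openly descriptive analysis. No alpha, p-value or hypothesis test appears, so *significant* may only mean clinically meaningful or beyond measurement error. That would make the MCID half largely a matter of wording. The reading does not fit the MDC, which says nothing about importance, and the sentence itself presents the rule as standing in for statistical analysis.

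Second, no wrong verdict is demonstrated. The MCID rule exceeds a one-sided 2.5% error rate only when the SD of change is above √n/1.96 = 1.77 × MCID (n = 12) or 1.35 × MCID (n = 7), and nothing shows that any outcome lies there. Over much of the plausible range the MDC is merely conservative: it misses real changes without creating false claims. This stands as a limit on size. It does not rescue a rule whose error rate is set by quantities that it ignores.

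Third, the means may be pooled over arms. With n = 19 the MDC limit is 1/√19 = 0.23 × MDC, the MCID limit is √19/2.101 = 2.07 × MCID, and the chance rates at SD = 2 and 3 × MCID are 1.5% and 7%. The problem is smaller but of the same kind. Also, 12 and 7 are the numbers allocated; the numbers assessed at each visit are not given. Dropout would widen the uncertainty.

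Fourth, separate intervals for each arm could invite a comparison of within-arm verdicts, and 6 outcomes × 3 visits × 2 arms gives 36 of them. That caution is fair and is carried into the fix. The missing between-arm estimate is a separate gap.

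**Conclusion.** The concern holds. As written, the rule can dismiss a real mean change when an MDC is used and can label a chance change significant when an MCID is used. The results as described do not let a reader correct either error.

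The direction follows from the text alone; the size does not. It rests on assumed ratios of the SD of change to the threshold, on a per-arm reading and on full attendance. If the SD of change is about equal to the MCID, false labels are rare. At two to three times the MCID they are not, and they are commoner in the arm of 7. The over-strictness of the MDC shrinks as people truly differ more in how much they change. This should be fixed before any change is reported as significant.

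**What to change.** 1. In Section 2, state that the thresholds are used to describe the size of changes, and drop the claim that they identify significant ones.
2. For each arm and visit, report the mean change from pre-treatment with its SD, the number of participants contributing and a 95% CI. Read the interval against zero for evidence of change, and set the mean beside the MCID for importance. Add that the two arms' intervals are not a comparison of the treatments and that, with 36 of them, some may exclude zero by chance.
3. Report the number and percentage in each arm whose own change exceeds the MDC (beyond measurement error) and, separately, the MCID (importance).
4. State the threshold value used for each outcome, or that none was found.

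The cost is SAP wording and a few more tables from data already collected. Some changes now called significant would be reported as uncertain, and the intervals in the arm of 7 will be wide.
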